### **2.2 SECONDARY OBJECTIVES**

To demonstrate the effects of dopaminergic activation with bromocriptine-QR on the regulation of plasma neuroendocrine factors such as the hypothalamic-pituitary-axis (HPA) hormones, and on the plasma levels of markers of inflammation and oxidative/nitrosative stress in type 2 diabetes subjects. The study will evaluate treatment effects on inflammatory markers, the leptin/adiponectin system, and hormonal levels of renin-angiotensin system (RAS), aldosterone and cortisol. Specifically, we will evaluate the following markers of inflammation and oxidative/nitrosative stress: 1) CRP, 2) IL6, 3) TNF  $\alpha$ , 4) PAI1, SOD, TBARS and ADMA and nitrotyrosine as well as other markers of oxidative/nitrosative stress. The study will evaluate the leptin/adiponectin system by measuring total adiponectin (TA), high molecular weight (HMW) adiponectin, leptin, and their ratios (TA/leptin and HMW adiponectin/leptin). A co-secondary objective of the study will be to assess the impact of bromocriptine-QR vs Placebo on measures of insulin resistance and glycemic control (e.g., OGTT glucose and insulin, Matsuda index, HOMA-IR, HbA1c).

The treatment effects on all of the above primary and secondary outcomes will also be assessed as a function of the duration of diabetes and other baseline demographics such as HbA1c, concomitant medications and metabolic status.

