
## **STUDY PROCEDURES**

**Fasting blood chemistries-** We will obtain blood samples using standard venipuncture techniques for determination of: Fasting serum glucose, HbA1c, and C-peptide (C-peptide may be non-fasting); lipid profile including total serum cholesterol, HDL, LDL, FFA and triglycerides; comprehensive metabolic panel including creatinine, AST and ALT; TSH, renin, angiotensin, aldosterone, ACTH, cortisol, prolactin, and serotonin. Oral glucose tolerance tests and HOMA measure of insulin resistance and beta cell function will also be determined. All of these assays are performed routinely by Sentara Healthcare System. We will also collect samples to assess markers

of inflammation and oxidative/nitrosative stress which include 1) CRP, 2) IL6, 3) TNF alpha, 4) PAI1, SOD, TBARS and ADMA and nitrotyrosine as well as other measures of oxidative/nitrosative stress. We will measure total adiponectin (TA), high molecular weight (HMW) adiponectin, leptin, and their ratios (TA/leptin and HMW adiponectin/leptin). The analyses of plasma markers of inflammation, oxidative/nitrosative stress, neuroendocrine factors and the adiponectin/leptin ratio will be conducted at Vero Science LLC (Tiverton, RI).

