### 7.3.2 **Secondary endpoint**

Secondary endpoints will be the evaluation of bromocriptine-QR's effects on inflammatory markers, neuroendocrine factors, markers of oxidative/nitrosative stress, the leptin/adiponectin system, and hormonal levels of renin-angiotensin system (RAS), aldosterone and cortisol. A co-secondary endpoint will be the impact of bromocriptine-QR vs Placebo on measures of insulin resistance and glycemic control (e.g., OGTT glucose and insulin, Matsuda index, HOMA-IR, HbA1c).

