bromocriptine-QR's impact to reduce elevated RHR was an independent predictor of its effect to reduce HbA1c among subjects with poor glycemic control (baseline HbA1c ≥ 7.5)⁴¹. The rationale for the categorical stratification of ≥ 70 or < 70 BPM for the analysis of the data from this current study is therefore based on the above considerations. A subset analysis will also be conducted in subjects with baseline RHR ≥ 80 BPM. We hypothesize that the treatment effect on SNS will be expressed in the RHR ≥ 70 BPM group.

Secondary Endpoints:

1) Measures of insulin resistance and glycemic control

Given the mechanism of action of Cycloset to improve postprandial insulin sensitivity, the main endpoint that will be evaluated is the effect of study drug treatment on postprandial glycemic control based on the OGTT plasma glucose and insulin data obtained at baseline and week 24. Between treatment group differences in change from baseline to week 24 for the area under the curve as well as levels at different time points of OGTT plasma glucose and insulin levels will be analyzed. Matsuda index of insulin sensitivity calculated using the OGTT glucose and insulin levels and HOMA-IR calculated from fasting glucose and insulin levels will also be analyzed as measures of insulin sensitivity/resistance.

All subjects completing 24-weeks of study drug treatment with data for baseline and week 24 OGTT will be included in the analyses of glycemic endpoints. The analyses will be done in the entire cohort of subjects with and without stratification by baseline HbA1c level of < 7.0 and ≥ 7.0 (i.e. suboptimal glycemic control).

Given that as a postprandial insulin sensitizer, the presence of adequate postprandial insulin levels is an important determinant of the postprandial glucose lowering efficacy, further subset analyses will be conducted to assess the above endpoints in subjects with OGTT insulin at T60 mins ≥ 50 $\mu\text{U/ml}$ and also in the subset on an insulin secretory agent (+/- TZD). An analysis stratified by duration of diabetes (≤ 4 years or > 4 years) may also be conducted depending on sample size.

2) Measures of inflammation, oxidative/nitrosative stress and plasma neuroendocrine factors

The following plasma factors will be evaluated: cortisol, aldosterone, norepinephrine, normetanephrine, adiponectin, leptin, IL6, TNF α , PAI1, SOD, TBARS, ADMA, nitrotyrosine and other appropriate factors of increased systemic inflammation and reactive oxygen species.

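### The SAP leaves out, without a reason, secondary outcomes that the protocol commits to compare between arms: change in HbA1c, renin and angiotensin, and HMW adiponectin with both leptin ratios; CRP is no longer named

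*SAP*

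**What the plan says.** **Protocol.** Section 7.3 commits to between-group analysis of change from baseline for all secondary endpoints.

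- *Glycaemic:* Section 7.3.2 lists measures of "insulin resistance and glycemic control (e.g., OGTT glucose and insulin, Matsuda index, HOMA-IR, HbA1c". HbA1c is also named in Section 2.2 and in the Outline's secondary objective.
- *Hormones:* Section 2.2 includes "hormonal levels of renin-angiotensin system (RAS), aldosterone and cortisol", as do the Outline and Section 7.3.2. The fasting blood chemistries under Study Procedures give the assays as "renin, angiotensin, aldosterone, ACTH, cortisol, prolactin, and serotonin".
- *Adipokines:* Section 2.2 names total adiponectin, HMW adiponectin, leptin and the ratio of each adiponectin measure to leptin. Section 7.3 assigns a laboratory for the adiponectin/leptin ratio.
- *Inflammation and oxidative stress:* CRP is the first marker listed in both the Outline's endpoints and Section 2.2.

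**SAP, Secondary Endpoints.**

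- Item 1 analyses OGTT glucose and insulin and the Matsuda index, and adds that "HOMA-IR calculated from fasting glucose and insulin levels will also be analyzed as measures of insulin sensitivity/resistance". HbA1c enters as a grouping variable: "The analyses will be done in the entire cohort of subjects with and without stratification by baseline HbA1c level of" below 7.0 or at least 7.0. Statistical Methods also lists baseline HbA1c as a possible adjustment factor. Change in HbA1c is not listed as an outcome.
- Item 2 begins "The following plasma factors will be evaluated: cortisol, aldosterone, norepinephrine, normetanephrine, adiponectin, leptin", continues with IL6, TNFα, PAI1, SOD, TBARS and ADMA, and ends with "nitrotyrosine and other appropriate factors of increased systemic inflammation and reactive oxygen species".

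**The concern.** The omitted items carry weight in the protocol's own argument. HbA1c is the protocol's named summary measure of glycaemic control, and the study schedule collects it at baseline, week 12 and week 24. The introduction proposes that the drug works partly by damping the renin-angiotensin system and the HPA axis. It also cites the team's earlier data linking adiponectin/leptin ratios to autonomic abnormality.

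If the SAP is followed literally, a favourable OGTT result could be reported with no HbA1c result beside it, and nothing would be reported on renin, angiotensin or the ratios. Because the changes are unexplained and the marker list ends in an open clause, a reader of the results could not separate outcomes planned from the start from those chosen later.

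**Working it through.** The check compares two lists. The plan's one design figure, power above 0.80 with 80 subjects, has no bearing on which outcomes are listed.

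**1. Protocol list.** Count items in the endpoint and objective text (Outline, Sections 2.2 and 7.3.2), taking the renin-angiotensin hormones as renin and angiotensin, the assays given under Study Procedures.

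**2. SAP list.** Plasma factors 13 plus glycaemic outcomes 4 = 17.

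**3. Match, reading the SAP's unqualified adiponectin as total adiponectin.**

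| Group | Protocol | In SAP | Absent from SAP |
|---|---|---|---|
| Inflammation, oxidative/nitrosative stress | 8 | 7 | CRP |
| Adiponectin/leptin | 5 | 2 | HMW adiponectin, total adiponectin/leptin, HMW adiponectin/leptin |
| Renin, angiotensin, aldosterone, cortisol | 4 | 2 | renin, angiotensin |
| Glycaemic | 5 | 4 | HbA1c |
| **Total** | **22** | **15** | **7** |

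22 − 15 = 7 absent. 17 − 15 = 2 newly named: norepinephrine and normetanephrine.

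ACTH, prolactin and serotonin are also missing from the SAP. They appear only in the protocol's assay list, so they are outside the 22.

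**4. Sensitivity to how items are counted.**

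- Renin-angiotensin as one item: 22 − 1 = 21 in the protocol, 7 − 1 = 6 absent.
- Also let the SAP's adiponectin cover the HMW form: 5 absent.
- Also let CRP return through the open clause: 4 absent.
- Also treat both ratios as derivable from listed analytes: 2 absent, namely HbA1c and the renin-angiotensin hormones other than aldosterone.

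The open clause cannot rescue those last two, because it is confined to inflammation and reactive oxygen species.

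**5. What restoring the seven does to multiplicity.** For scale only, assume independent outcomes each tested at 0.05. The chance of at least one false positive is 1 − 0.95^17 = 0.58 for the SAP's 17 outcomes. For 17 + 7 = 24 it is 1 − 0.95^24 = 0.71. These markers are correlated, so the figures are illustrative, and they ignore the strata by resting heart rate and HbA1c.

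**6. Whether the week-24 data will exist.** The study schedule marks neuroendocrine markers at week 24. The Visit 4 blood list in Section 7.2.2.10 names inflammatory and oxidative/nitrosative markers but not neuroendocrine factors, although it refers to the schedule. HbA1c is in both places. The mismatch touches renin and angiotensin, and also the cortisol and aldosterone that the SAP keeps.

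**The case against.** The strongest defence has five parts.

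- **The protocol's wording is loose.** HbA1c follows an e.g. and is absent from the Outline's endpoint section. The ratios are in the objectives, not the endpoint sections. This is true, but HbA1c is named in three places as a measure of this endpoint, and Section 2.2 says which adipokine quantities will be measured.
- **The SAP explains its glycaemic focus.** It makes post-challenge control the main glycaemic outcome because of the drug's mechanism. That justifies a ranking. It does not explain leaving HbA1c out while keeping Matsuda and HOMA-IR.
- **The open clause fills the gap, and the protocol had one too.** It could readmit CRP, so CRP is unnamed rather than clearly dropped. The protocol's clause covered oxidative/nitrosative markers; the SAP widens it to systemic inflammation. It does not reach HbA1c, renin or angiotensin.
- **The additions are legitimate.** Norepinephrine and normetanephrine are added by name, not through the open clause. They fit the protocol's generic neuroendocrine class, and the introduction discusses norepinephrine. This stands: they are newly specified, not foreign to the protocol.
- **Aldosterone already represents the renin-angiotensin system.** In part. But the protocol lists that system alongside aldosterone and specifies renin and angiotensin assays.

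On timing, the SAP is dated 14 December 2018, about four months after the planned last-subject finish of August 2018. A reader might infer that outcomes were chosen after looking at results. The documents do not support that. August 2018 is a planned date that Section 3.2 allows to vary, the protocol permits the SAP to be finalised up to database lock, and nothing shows lock or unblinding by that date.

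**Conclusion.** The point holds as a contradiction between protocol and SAP on secondary outcomes. Seven of 22 items are absent by name and no reason is given. HbA1c and renin/angiotensin are missing however the items are counted. CRP is left to discretion.

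A reader might go further and say that the secondary objectives go unanswered, or that ACTH, prolactin and serotonin were dropped as endpoints. Neither is supported. The glycaemic objective keeps four outcomes and the plasma objective keeps 11 of the protocol's named markers, so what is lost is part of each. The three hormones were never individually named as endpoints. Selective reporting cannot be excluded on these documents, but it is not shown.

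The count rests on two conventions: renin and angiotensin as separate items, and the SAP's adiponectin read as total adiponectin. The primary endpoint is unaffected. This should be corrected, but it does not threaten the trial's main analysis.

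**What to change.** In the SAP's Secondary Endpoints:

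1. Add the between-arm change from baseline to week 24, with estimate and confidence interval, for HbA1c, CRP, renin, angiotensin, HMW adiponectin, total adiponectin/leptin and HMW adiponectin/leptin.
2. Add a short table marking each protocol-named outcome as kept, dropped or added, with the reason. Say so where an assay was not run, and account for ACTH, prolactin and serotonin as assay-list items.
3. Label norepinephrine and normetanephrine as specified after the protocol, and label any marker entering through the open clause as exploratory.
4. Reconcile the Visit 4 blood list with the study schedule on neuroendocrine markers, and state what was drawn at week 24.
5. State who contributes to the HbA1c analysis, since the SAP's glycaemic set requires OGTT data at both baseline and week 24.

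The cost is SAP wording, a few table rows and the extra secondary comparisons sized above. HbA1c needs no new sampling. Recovery of renin and angiotensin at week 24 depends on item 4, so it should not be assumed to be free.

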## **7.3 STATISTICAL METHODS**

Statistical analyses will be conducted on between group (bromocriptine-QR vs. placebo) differences in change from baseline of all primary and secondary endpoints. The treatment effects on all of the primary and secondary outcomes will also be assessed as a function of the duration of diabetes and other baseline demographics such as HbA1c, concomitant medications and metabolic status. Mean differences of glycemic control, various derivative autonomic function values, and inflammatory marker levels will be compared first using standard Analysis of Variance (ANOVA), with diagnostic group entered as the predictor variable. Within-group analysis for change in primary and secondary endpoints after 12 weeks of treatment will be done using repeated measures MANOVA (multivariate analysis of variance). For glycemic control analysis patients will be stratified according to post-prandial insulin response. If data are not normally distributed, the Wilcoxon signed-rank (within group) or Mann Whitney (between group) tests may be employed or Fisher's exact test in case of small sample sizes. The level of significance will be set at  $p < 0.05$ . Relationships and/or trends between the effect of Cycloset on neurovascular function and diabetic neuropathy will be determined with Spearman's rank correlation.

A statistical analysis plan (SAP), providing details of the analyses and presentation structure of the results, will be developed and finalized before the database is locked.

A local laboratory will be utilized for collection and analysis of the laboratory tests associated with efficacy, and safety. Standardized guidelines for preparation, collection, and centralized analysis of blood specimens will provide uniformity of the data and will avoid potential inter-laboratory variability due to inconsistent methodology.

The analyses of plasma markers of inflammation, oxidative/nitrosative stress, neuroendocrine factors, and the adiponectin/leptin ratio will be conducted at VeroScience (Tiverton, RI).

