Impact of Timed Bromocriptine-QR Therapy upon Measures of Sympathetic Tone and Vascular Biology in Type 2 Diabetes Subjects

Statistical Analysis Plan

Date: Dec 14, 2018

Study Objectives:

Primary Objective:

To demonstrate the effects of dopaminergic activation with bromocriptine-QR on the autonomic nervous system in subjects with type 2 diabetes.

Secondary Objectives:

The Co-secondary objectives of the study were the following:

- 1) To assess the impact of bromocriptine-QR vs placebo on measures of insulin resistance and glycemic control
- 2) To demonstrate the effects of dopaminergic activation with bromocriptine-QR on the regulation of plasma neuroendocrine factors such as the hypothalamic-pituitary-axis (HPA) hormones, and on the plasma levels of markers of inflammation and oxidative/nitrosative stress in type 2 diabetes subjects.

Study Endpoints and Analysis Plan

Primary Endpoint

Changes in autonomic function measures from baseline to week 24 following treatment with study drug (bromocriptine-QR or placebo).

The effect of treatment with study drug for 24 weeks on the following three measures of autonomic function will be analyzed:

- 1) Heart Rate Variability
- 2) Resting Heart Rate
- 3) Sudorimetry

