Between treatment group differences in the change from baseline to week 24 in the above autonomic function parameters will be analyzed. All analyses will be stratified by baseline resting heart rate (RHR) ≥ 70 or < 70 beats per min (BPM) (see below). The rationale for such stratification is as follows. Elevated RHR is known to be a simple and useful clinical measure of elevated sympathetic nervous system activity as it reflects central sympathetic-parasympathetic activity balance^{1,2} and has been shown to correlate with other measures of SNS activity such as muscle sympathetic nerve activity and serum noradrenalin levels and heart rate variability³⁻⁶. While clinically, RHR between 60-100 BPM is considered the “normal” range for RHR and RHR ≥ 100 is used as the criteria for defining tachycardia, a large body of evidence from epidemiological and clinical studies suggest that increasing RHR even within the “normal” range is associated with increased cardiometabolic risk, particularly above around 70, likely reflecting the deleterious effects of underlying elevated sympathetic tone leading to such elevated RHR. Such elevated RHR has been associated with insulin resistance^{7,8}, altered beta cell function⁹, impaired glucose regulation and increased risk of developing type 2 diabetes mellitus¹⁰⁻¹² as well as increased cardiovascular risk¹³⁻³¹ and mortality^{13-23,26,27,29,31-40}. In addition to and consistent with the reported evidence supporting elevated RHR threshold of approximately 70 BPM as an indicator of elevated sympathetic tone, a previous study that evaluated the effect of bromocriptine-QR on RHR in subjects with type 2 diabetes demonstrated that bromocriptine-QR’s influence to reduce RHR is only observable if the RHR is elevated to ≥ 70 BPM and the magnitude of this reduction was greater the more elevated the baseline RHR was above 70 BPM with greater reductions seen with baseline RHR ≥ 80 ^{41,42}. Furthermore, it was observed that the degree of

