Between treatment group differences in the change from baseline to week 24 in the levels of the above factors will be analyzed in the overall cohort as well as with stratification by baseline RHR ($< \geq 70$ BPM) as described above for the analysis of autonomic function markers as well as stratification by baseline HbA1c ($< \geq 7.0$) as described above for the analysis of glycemic control parameters.

Statistical Methods:

Between treatment group (bromocriptine-QR vs. placebo) differences in change from baseline to week 24 and within group changes from baseline to week 24 of all primary and secondary endpoints will be analyzed using Independent Samples T-tests. If the data are not normally distributed in raw form or in some cases after simple log transformation, then appropriate non-parametric tests will be used instead. Within group analyses will be performed using paired samples T-test or repeated measures ANOVA as appropriate. The treatment effects on the primary and secondary outcomes will also be assessed after adjustment as needed for other potential factors that could influence the specific endpoint being analyzed such as duration of diabetes, baseline HbA1c, baseline RHR and/or change in RHR from baseline, concomitant medications and other baseline demographics as appropriate using categorical stratified analyses as discussed above and/or multivariable regression analyses methods.

References:

4. Egan BM: Insulin resistance and the sympathetic nervous system. *Curr Hypertens Rep* 2003;5:247-254

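### The main between-arm test is an unadjusted t-test on change, which is unbiased but less precise than baseline-adjusted ANCOVA; separately, the optional adjusted treatment effects may condition on change in resting heart rate, a post-randomisation primary measure

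*SAP*

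**What the plan says.** The SAP's Statistical Methods section states that differences between arms in change from baseline to week 24 "of all primary and secondary endpoints will be analyzed using Independent Samples T-tests", with log-transformation or non-parametric tests if normality fails. Neither document specifies an ANCOVA on the endpoint's own baseline; Protocol 7.3 also compares change from baseline, by ANOVA. Under Primary Endpoint, the SAP adds: "All analyses will be stratified by baseline resting heart rate", at 70 beats per minute.

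Statistical Methods then adds a second layer: "The treatment effects on the primary and secondary outcomes will also be assessed after adjustment as needed", for factors that could influence the endpoint. The list of examples includes "baseline RHR and/or change in RHR from baseline, concomitant medications and other baseline demographics as appropriate", and the methods are stratified analyses or multivariable regression.

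Three other places bear on that list.
- The SAP's primary measures include "2) Resting Heart Rate".
- Its rationale for stratifying cites an earlier study in which the drug's "influence to reduce RHR is only observable if the RHR is elevated to ≥ 70 BPM", and concludes: "We hypothesize that the treatment effect on SNS will be expressed in the RHR ≥ 70 BPM group".
- Protocol 7.3 says treatment effects will be "assessed as a function of the duration of diabetes and other baseline demographics such as HbA1c, concomitant medications and metabolic status". The same wording is in the Protocol Outline and Section 2.2.

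**The concern.** There are two separate issues, and the second carries more weight.

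**Precision.** A t-test on change makes no use of the correlation between an endpoint's baseline and its week-24 value, beyond the subtraction itself. In a trial of 80 whose autonomic analyses are split again at RHR 70, the confidence intervals will be wider than the collected data allow.

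**Conditioning on an outcome.** Change in RHR is measured after randomisation, is itself a primary measure, and is something the SAP expects the drug to alter. A regression that holds it fixed removes whatever part of the drug's effect is associated with the RHR response, and it breaks the randomised comparison for the remainder. The SAP calls the result a treatment effect and does not label it as mediation. At stake is how a supplementary estimate would be read, in the subgroup where the SAP expects benefit.

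**Working it through.** **The plan's own figure.** Protocol 9.7 claims power above 0.80 with 80 participants for a 10% change. It gives no SD, so the figure cannot be reproduced. With 40 per arm and two-sided 0.05 (sidedness is not stated), 80% power needs a standardised difference of (1.960 + 0.842) × √(2/40) = 0.626. For a 10% difference the SD of change would have to be about 10/0.626 = 16% of baseline.

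**Precision, whole cohort.** Assume equal SDs s at baseline and week 24, with correlation r.
- Variance of change: 2(1 − r)s².
- Residual variance under ANCOVA: (1 − r²)s².
- Ratio, t-test to ANCOVA: 2/(1 + r).
- The t-test on 80 is about as precise as ANCOVA on 80(1 + r)/2.

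**Precision, within RHR strata.** Splitting on RHR already narrows the spread of baseline. If the within-stratum baseline variance is v times the overall variance, the ratio is 1 + v(1 − r)/(1 + r). For RHR itself, a normal median split gives v = 1 − 2/π = 0.363. For HRV and sudorimetry, v = 1 − 0.637q², where q is the correlation of that endpoint's baseline with baseline RHR. With q from 0 to 0.5, v runs from 1 to 0.841.

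| r (assumed) | Whole cohort ratio | 80 on t-test ≈ ANCOVA on | RHR within strata | HRV, sudorimetry within strata |
|---|---|---|---|---|
| 0.3 | 1.54 | 52 | 1.20 | 1.54–1.45 |
| 0.5 | 1.33 | 60 | 1.12 | 1.33–1.28 |
| 0.7 | 1.18 | 68 | 1.06 | 1.18–1.15 |
| 0.9 | 1.05 | 76 | 1.02 | 1.05–1.04 |

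The whole-cohort columns apply to secondary endpoints, which the SAP also analyses unstratified; the last two apply to the primary measures. As a guide to power, a t-test with power 0.80 becomes ANCOVA with power 0.90 at r = 0.5 in the whole cohort, since 2.802/√0.75 − 1.960 = 1.275. In simulation at r = 0.5 both methods recovered the true effect, so the difference is precision only.

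**Adjusting for RHR change.** Work in within-arm SD units of change. Let dY be the true effect on the endpoint, dR the drug's effect on RHR change, and b the within-arm slope of the endpoint on RHR change. Then

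adjusted coefficient = dY − b × dR.

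Take dR = −0.5 and dY = −0.3 (both assumed):
- b = +0.3: −0.30 + 0.15 = −0.15
- b = +0.5: −0.30 + 0.25 = −0.05
- b = −0.3: −0.30 − 0.15 = −0.45
- b = −0.5: −0.30 − 0.25 = −0.55
- b = 0, or dR = 0: −0.30, no shift

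**False positives when dY = 0** (simulated, two-sided 0.05, |b| from 0.3 to 0.5):
- RHR ≥70 stratum, 20 per arm, all treated subjects shifting 0.5 SD: about 7% to 14%.
- Whole cohort, 40 per arm, half of subjects at ≥70 and only those shifting when treated: about 6% to 10%.

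**The case against.** The t-test is a legitimate analysis, consistent with the protocol's own comparison of change, and the gain from ANCOVA rests on a correlation that neither document supplies. Within the RHR strata the gain for RHR is negligible at high r (1.02 at r = 0.9). The SAP also already permits regression on baseline RHR and baseline HbA1c, which are own baselines for those variables. All of this stands, and it makes the first issue one of efficiency. It does not remove it: the permitted adjustment is optional, and HRV and sudorimetry gain little own-baseline adjustment from an RHR split.

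On the second issue, the RHR adjustment is supplementary and discretionary. The SAP does not say it will be run for any given endpoint or how it would be presented. The protocol's Introduction also states mechanistic aims: relating change in autonomic balance to postprandial glucose and to oxidative and nitrosative stress. Those aims justify a mechanistic analysis; they do not justify presenting its coefficient as an adjusted treatment effect.

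Four stronger readings are tempting and are not supported.
- A reader might infer that the SAP breaks a protocol limit on covariates. The protocol's factors are framed as baseline characteristics, but they are introduced as examples and contain no limiting words.
- A reader might infer that a true glycaemic benefit will be pulled toward zero. The SAP cites only an earlier-study association between RHR reduction and HbA1c reduction, at baseline HbA1c of 7.5 or more. It gives no slope for the OGTT measures, Matsuda index or HOMA-IR that it lists as glycaemic endpoints. The most that follows is that it could be.
- A reader might compute a false-positive rate of up to 23% at 40 per arm. That requires every treated subject to shift by 0.5 SD, contrary to the SAP's premise that only those at RHR ≥70 respond.
- A reader might infer that the main result is biased. The unadjusted between-arm test does not involve RHR change.

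**Conclusion.** Both issues hold, at the level of a recommended change. The t-test on change is unbiased under randomisation; its fault is lost precision, with a variance 1.05 to 1.54 times that of ANCOVA in the whole cohort for r from 0.9 down to 0.3. The range is smaller for RHR within its own strata (1.02 to 1.20) and close to the whole-cohort range for HRV and sudorimetry.

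The optional adjustment for RHR change yields a coefficient that is not the treatment effect wherever two conditions both hold: the drug moves RHR, and RHR change is related to the endpoint. The shift can go either way. If either condition fails there is none, and on the SAP's premise little is expected below 70.

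The sizes rest on assumed correlations, slopes, stratum shares and a 0.5 SD fall in RHR. The documents give none of these, so the figures illustrate and do not predict. The direction of the argument does not depend on them.

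**What to change.** 1. Make the between-arm analysis of each continuous endpoint an ANCOVA of the week-24 value (or change) on treatment and that endpoint's own baseline, fitted within the planned RHR strata or with a treatment-by-stratum term. Keep the log-transform and non-parametric fallback, and say whether the fallback is a rank ANCOVA, since otherwise it loses the baseline adjustment.
2. Delete RHR change from the covariate list, so that treatment-effect models use pre-randomisation variables only. Report any model containing RHR change as a separately labelled exploratory mediation analysis, which serves the protocol's mechanistic aims.

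The cost is two SAP sentences and a little extra analysis, with no new data. The change should be dated before the treatment code is opened. If the code is already open, keep the t-test as planned, report ANCOVA as a labelled sensitivity analysis, and label RHR-change models as exploratory mediation.

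### Within-arm tests of resting heart rate, in strata cut on baseline resting heart rate, do not hold their nominal error rate because of regression to the mean

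*SAP*

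**What the plan says.** The SAP's Primary Endpoint section names three autonomic measures, each analysed as a 24-week change: heart rate variability, "Resting Heart Rate" and sudorimetry. It then states: "All analyses will be stratified by baseline resting heart rate (RHR) ≥ 70 or < 70 beats per min (BPM"). It adds: "A subset analysis will also be conducted in subjects with baseline RHR ≥ 80 BPM".

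The expected result is also stated: "We hypothesize that the treatment effect on SNS will be expressed in the RHR ≥ 70 BPM group". The supporting rationale cites earlier work in which the drug lowered RHR only when it started at 70 or more, and by more at higher starting values.

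The SAP's Statistical Methods section covers both between-arm differences and within-group changes, for every primary and secondary endpoint. For the latter it says: "Within group analyses will be performed using paired samples T-test or repeated measures ANOVA as appropriate". An earlier sentence in the same paragraph assigns within-group changes to independent-samples t-tests, together with the between-arm comparisons. Adjustment for baseline RHR is offered only as needed.

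Neither document mentions regression to the mean, says which reading or average supplies the stratifying value, or limits within-arm results to description. The protocol's Study Schedule and its Visit 1 list have no separate RHR item.

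**The concern.** RHR is both the variable that selects the stratum and an outcome tested within it. A single RHR value combines the subject's usual level with day-to-day variation. Subjects chosen because their baseline was high were, on average, somewhat above their usual level that day, and the week-24 value will tend to come back down. The reverse holds for subjects chosen because they were low.

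A paired test in one arm reads that return as change. In the 70-and-above stratum and the 80-and-above subset it has the sign, and the gradient, that the SAP expects from the drug. For this endpoint, a within-arm test in these strata therefore cannot separate the hypothesis from the artefact. The practical risk is a report of a significant fall on bromocriptine-QR, not matched by significance on placebo, taken as support for the stated hypothesis.

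**Working it through.** **The plan's own figures.** The documents give no expected within-stratum change and no error rate for these tests. The only related figure is the power above 0.80 with 80 subjects for a 10% change (protocol section 9.7). No SD is stated, so it can be neither reproduced nor refuted: at 40 per arm and two-sided 0.05, a between-arm test has that power only if the SD of the percentage change is at most about 16%.

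**Inputs from the documents.** Cut-offs of 70 and 80 BPM (SAP, Primary Endpoint); about 40 per arm and significance at 0.05 (protocol 9.7). Sidedness is not stated and is taken as two-sided, so a valid test gives a significant fall in 2.5% of null trials.

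**Assumed inputs.** Baseline RHR mean 68–75 BPM, SD 8–12, correlation between baseline and week 24 (ρ) 0.5–0.9, bivariate normal, no drug effect and no time trend. The stratifying value is also the baseline for change.

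**Step 1: expected null change.** With a = (cut-off − mean)/SD, and φ and Φ the standard normal density and distribution function:

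- at or above the cut-off: −(1 − ρ) × SD × φ(a)/(1 − Φ(a))
- below the cut-off: +(1 − ρ) × SD × φ(a)/Φ(a)

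For mean 70, SD 10, ρ = 0.7:

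- 70 or above: a = 0, ratio 0.798, change −0.3 × 10 × 0.798 = −2.4 BPM
- below 70: +2.4 BPM
- 80 or above: a = 1, ratio 1.525, change −0.3 × 10 × 1.525 = −4.6 BPM

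For scale, the mean baseline in the upper stratum is then 70 + 10 × 0.798 = 78.0 BPM. A 10% change is 7.8 BPM, so the artefact is about 2.4/7.8 = 31% of it.

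Over the whole assumed range:

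| Group | Expected null change (BPM) |
|---|---|
| 70 or above | −0.4 to −5.4 |
| below 70 | +0.5 to +6.5 |
| 80 or above | −1.0 to −9.2 |

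The direction needs none of these figures. With a stable distribution over time, any correlation below 1 gives these signs.

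**Step 2: error rate of the tests.** Null trials were simulated with 40 per arm, 6,000 trials per setting, SD 10. The table shows the share with a significant fall in the bromocriptine-QR arm, by paired t-test.

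| Mean | ρ | 70 or above | 80 or above |
|---|---|---|---|
| 70 | 0.5 | 0.45 | 0.41 |
| 70 | 0.7 | 0.28 | 0.26 |
| 70 | 0.9 | 0.11 | 0.10 |
| 75 | 0.5 | 0.28 | 0.52 |
| 75 | 0.7 | 0.18 | 0.32 |
| 75 | 0.9 | 0.09 | 0.13 |

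At mean 70 and ρ = 0.7, SD 8 or 12 leaves the 70-and-above rate at 0.28, and 30 completers per arm lower it to 0.22. A mean of 68 gives somewhat higher rates, and the opposite corner (mean 75, SD 8, ρ = 0.9) slightly lower ones. The range of 9–45% is therefore approximate, not a pair of limits.

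**Step 3: one arm significant, the other not.** In the 70-and-above stratum, a significant fall on drug with no significant change on placebo occurs in about 20% of null trials at mean 70 and ρ = 0.7, and in 8–25% across the settings.

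**Step 4: the comparisons that are sound.** The between-arm t-test of change rejects in 0.046–0.054 of null trials at 70 or above, and in 0.047–0.058 below 70. The paired test in a whole, unselected arm rejects in 0.045–0.052.

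**The case against.** The strongest reply is that efficacy is defined between arms. The Primary Endpoint section sets out between-group differences in change just before it introduces the stratification, and protocol section 7.3 opens the same way. Both arms regress alike, so that comparison is protected. This stands, and it confines the problem to the within-arm tests. It does not rescue them, because a paired test inside one arm has no control to subtract.

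It can also be said that no single sentence announces within-arm RHR tests by stratum. They follow from combining the rule that all analyses are stratified with within-group testing of every primary endpoint. That is the plain reading, but it is a reading.

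The documents also do not say that stratum and baseline come from the same measurement. Averaged readings would raise the correlation and shrink the artefact: at ρ = 0.9 the rate in the upper stratum is 0.09–0.11, still well above 0.025.

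A reader might go further and infer that the trial is bound to show a false effect, or that its design favours the drug. The documents support neither. The shift is certain only in expectation, and more than half of null trials show no significant fall in the upper stratum at the settings in the table. With no drug effect, significance on placebo alone is as likely as on drug alone. A real time trend could add to the shift or offset it.

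**Conclusion.** The point holds for the within-arm tests of RHR in the RHR strata, and only there. Their direction of error is fixed by the design and coincides with the SAP's hypothesis at 70 or above and at 80 or above. The size rests on an assumed mean, SD and correlation, and on one value serving as both stratifier and baseline: an expected −0.4 to −5.4 BPM in the upper stratum, with a false significant fall in roughly 9–45% of null trials instead of 2.5%. The randomised between-arm comparison within strata is sound at about 5%, so the main efficacy analysis is not undermined. The change should be made because the plan names a test with the wrong error rate and does not limit how its result may be used.

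**What to change.** In the SAP's Statistical Methods:

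1. State that within-arm RHR changes in the 70-and-above, below-70 and 80-and-above groups are descriptive, shown as mean and confidence interval with placebo alongside and no p-value, and that no efficacy claim rests on them.
2. Base inference in these groups on the drug-minus-placebo difference in change, adjusted for continuous baseline RHR. Make that adjustment fixed, not optional.
3. Reconcile the two sentences that assign within-group changes first to independent-samples and then to paired tests.

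The cost is wording only, plus the loss of within-arm p-values in these strata. No data collection changes.

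Defining the stratum from the screening ECG is not a good substitute. If, by assumption, screening correlates 0.8 with Visit 1 and 0.7 with week 24 (mean 72, SD 10), a null fall of (0.8 − 0.7) × 10 × 0.675 = 0.7 BPM remains at 70 or above, and 0.1 × 10 × 1.367 = 1.4 BPM at 80 or above. It would also change the stratum definition.
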